9.5 Monitoring, second paragraph

At the earlier of a) approximately 6 months after the first participant begins study treatment and b) after 12 participants have reached 12 weeks of study treatment, a Study Monitoring Committee (SMC) will be convened to review the study data and progress according to ACTG Standard Operating Procedures. The SMC will review accrual, participant characteristics, AE summaries (and listings detailing each team decision as to the relationship of the AE to study treatment), sirolimus dosages and trough levels (in particular for any participant with a Grade 3 or higher AE), CD4+ cell counts and HIV-1 RNA levels/suppression over time, off-treatment and off-study rates (and reasons) and completeness of sample availability. In addition, if there are any Grade 4 AEs or greater than three Grade 3 AEs attributed to study treatment in two or more participants per section 9.2.1.1, ~~sirolimus use in all participants will be stopped and an SMC safety review will be conducted and a conference call held if deemed necessary by the SMC within 7 business days of receiving the safety report from the team. Sirolimus use in participants will continue while the SMC safety review is conducted. The SMC review will include an assessment of the safety of the continued use of sirolimus by study participants as well as deliberations regarding other modifications to the study to assure the safety of the participants.~~ With respect to monitoring AEs, any lipid laboratory value/abnormality will be considered as a single event, rather than separate events for each individual test (including fasting triglycerides, LDL, and total cholesterol). An SMC review will also be triggered if more than 25% of participants (evaluating at least 12 participants, e.g., greater than 3 of 12) discontinue study treatment due to AEs or other side effects attributable to study drug; the therapeutic duration of the trial might be reduced to 12 weeks or otherwise modified following SMC review. Subsequent SMC reviews will be approximately every 6 months. In addition, the core team or the SMC, at any time it thinks appropriate, may ask for the SMC to independently review all available safety data.

Clarification Memorandum #2 for:

A5337

**Safety and Efficacy of Sirolimus for HIV Reservoir Reduction in Individuals on
Suppressive Antiretroviral Therapy**

A Limited Center Trial of the AIDS Clinical Trials Group (ACTG)

DAIDS ES # 11981

9.5 Monitoring, second paragraph

At the earlier of a) approximately 6 months after the first participant begins study treatment and b) after 12 participants have reached 12 weeks of study treatment, a Study Monitoring Committee (SMC) will be convened to review the study data and progress according to ACTG Standard Operating Procedures. The SMC will review accrual, participant characteristics, AE summaries (and listings detailing each team decision as to the relationship of the AE to study treatment), sirolimus dosages and trough levels (in particular for any participant with a Grade 3 or higher AE), CD4+ cell counts and HIV-1 RNA levels/suppression over time, off-treatment and off-study rates (and reasons) and completeness of sample availability. In addition, sirolimus use in all participants will be stopped and an SMC safety review will be promptly convened if there are any Grade 4 AEs or greater than three Grade 3 AEs attributed to study treatment in two or more participants per section 9.2.1.1. **With respect to monitoring AEs, any lipid laboratory value/abnormality will be considered as a single event, rather than separate events for each individual test (including fasting triglycerides, LDL, and total cholesterol).** An SMC review will also be triggered if more than 25% of participants (evaluating at least 12 participants, e.g., greater than 3 of 12) discontinue study treatment due to AEs or other side effects attributable to study drug; the therapeutic duration of the trial might be reduced to 12 weeks or otherwise modified following SMC review. Subsequent SMC reviews will be approximately every 6 months. In addition, the core team or the SMC, at any time it thinks appropriate, may ask for the SMC to independently review all available safety data.

Clarification Memorandum #1 for:

A5337

**Safety and Efficacy of Sirolimus for HIV Reservoir Reduction in Individuals on
Suppressive Antiretroviral Therapy**

A Limited Center Trial of the AIDS Clinical Trials Group (ACTG)

DAIDS ES # 11981

Clarification Memorandum Date: 4 October 2016

ACTG Network Coordinating Center

Social & Scientific Systems, Inc.
[name]
[name] 20910

[contact]
[contact]

CLARIFICATION MEMO

DATE: October 4, 2016
TO: ACTG CTU Principal Investigators, CRS Leaders, and CTU/CRS Coordinators
FROM: A5337 Protocol Team
SUBJECT: Clarification Memo #1 for Protocol A5337, Version 2.0, 07/18/16, entitled, "Safety and Efficacy of Sirolimus for HIV Reservoir Reduction in Individuals on Suppressive Antiretroviral Therapy"

This clarification memo does not result in a change in the protocol informed consent document. The Division of AIDS does not require you to forward it to your institutional review board (IRB); however, as always, you must follow your IRB's policies and procedures. If IRB review of clarification memos is required at your site, please submit this document for review.

Each site should file a copy of this clarification memo with the protocol for reference.

The protocol clarifications contained in this memo should be implemented immediately. These updates will be included in the next version of the A5337 protocol if it is amended at a future date.

The following are clarifications (in bold) to protocol A5337, Version 2.0, 07/18/16:

- 4.2.16 Herpes-zoster or varicella-zoster viral infection requiring treatment within 90 days prior to study entry or currently on suppressive therapy **for herpes-zoster (varicella-zoster)**.

NOTE: Suppressive therapy for herpes simplex viruses 1 or 2 is not exclusionary.

5.1 Regimens, Administration and Duration

Participants taking a non-PI, non-NNRTI containing regimen, and those on a non-PI, RPV-based regimen, will initially receive:

- Sirolimus 0.025 mg/kg/day administered orally once daily with or without food. See Table 2.

Participants taking an NNRTI containing regimen (with the exception of RPV) will initially receive:

- Sirolimus 0.05 mg/kg/day administered orally once daily with or without food. See Table 3.

In order to achieve therapeutic levels, therapy will be initiated with the dosage noted above and dosing will be subsequently adjusted based on trough blood sirolimus concentrations to achieve target concentrations between 5 and 10 ng/mL (see Table 4). A detailed dosing table based on the adjustment algorithm in Table 4 can be found on the A5337 PSWP.

NOTE: If there is a change in ART regimen between entry and week 12, the site must contact the A5337 core team ([contact]) as soon as possible to reassess the initial sirolimus dose based on current ART regimen/classification at week 12.

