2.1.10 Sirolimus metabolism and drug-drug interactions

Sirolimus is usually avoided with concomitant use of strong inducers (e.g., rifampin and rifabutin) and strong inhibitors (e.g., ketoconazole, voriconazole, itraconazole, erythromycin, and clarithromycin) of CYP3A4 and P-gp. Grapefruit juice is also contraindicated during sirolimus therapy. Drugs that could increase sirolimus blood concentrations include cimetidine, cisapride, clotrimazole, diltiazem, fluconazole, PIs (including those used to treat HIV and HCV), metoclopramide, nicardipine, troleandomycin and verapamil (verapamil levels may also increase when given with sirolimus). Drugs that could decrease sirolimus concentrations include carbamazepine, phenobarbital, phenytoin, rifapentine, NNRTIs and St. John's wort.

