proposed will be sufficient to overcome potential interactions [55,56]. In the recent sirolimus monotherapy study for KS, the three participants who were on suppressive NNRTI regimens without PIs had maximum drug trough levels of 7 to 13, all of which are in or near the accepted, safe therapeutic range used for transplant rejection [14]. Furthermore, these participants were on steady-state doses of sirolimus that mirror those of HIV-negative participants not on ART. The exact effects of sirolimus on NNRTI or NRTI levels are not well described, but all participants, even those on PI-based regimens with inconsistent drug levels, had stable, sustained viral control during sirolimus treatment [14].

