5.0 STUDY TREATMENT

5.1 Regimens, Administration and Duration

Eligible **participants** will be stratified at study entry by class of ART regimen as follows:

Participants taking a non-PI, non-NNRTI containing regimen, and those on a non-PI, RPV-based regimen, will initially receive:

- Sirolimus 0.025 mg/kg/day administered orally once daily with or without food. See Table 2.

Participants taking an NNRTI containing regimen (with the exception of RPV) will initially receive:

- Sirolimus 0.05 mg/kg/day administered orally once daily with or without food. See Table 3.

In order to achieve therapeutic levels, therapy will be initiated with the dosage noted above and dosing will be subsequently adjusted based on trough blood sirolimus concentrations to achieve target concentrations between 5 and 10 ng/mL (see **Table 4**). A detailed dosing table based on the adjustment algorithm in **Table 4** can be found on the A5337 PSWP.

Table 2. Sirolimus Dosing at 0.025mg/kg			
Weight	Initial daily dose	25% increase*	25% reduction*
50 to 70 kg	1.5 mg	2 mg	1 mg
71 to 90 kg	2.0 mg	2.5 mg	1.5 mg
91 to 110 kg**	2.5 mg	3 mg	2.0 mg

*Dose adjustment based on sirolimus trough level.

**For participants weighing >110 kg, the sirolimus dose needs to be clarified by the team.

Table 3. Sirolimus Dosing at 0.05mg/kg			
Weight	Initial daily dose	25% increase*	25% reduction*
50 to 70 kg	3 mg	4 mg	2 mg
71 to 90 kg	4 mg	5 mg	3 mg
91 to 110 kg**	5 mg	6.5 mg	4 mg

*Dose adjustment based on sirolimus trough level

**For participants weighing >110 kg, the sirolimus dose needs to be clarified by the team.

Table 4. Sirolimus Dose Adjustment Algorithm	
Sirolimus level	Dose adjustment*
<5 ng/mL	Increase dose by 25%,
5-10 ng/mL	Continue current dose
>10, <15 ng/mL	Reduce dose by 25%
>15, <20/ng/mL	Hold dose for 48 hours, then decrease dose by 25%
>20/ng/mL	Hold dose until next level check, if <12 ng/mL, then restart study drug at 50% prior dose

*Round dose up to closest sirolimus 0.5mg tablet. Sirolimus tablets cannot be split, crushed or chewed.

Participants will initiate study treatment at week 12 and continue for 20 weeks.

Participants will be followed off-treatment for an additional 12 weeks for a total of 44 weeks. Treatment must be initiated within 72 hours of week 12 (day 0) evaluations (see section 6.2.3).

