5.4 Concomitant Medications

Whenever a concomitant medication or study agent is initiated or a dose changed, investigators must review the concomitant medication's and study agent's most recent package insert, Investigator's Brochure, or updated information from DAIDS to obtain the most current information on drug interactions, contraindications, and precautions.

Additional drug information may be found on the updated **ACTG Precautionary and Prohibited Medications** Database located at:
http://tprc.pharm.buffalo.edu/home/di_search/

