5.4.1 Required Medications

Continuous ART, defined as active therapy with no treatment interruption longer than 7 consecutive days and a total duration off ART of no more than 7 days, is required through week 44. Changes in the regimen are allowed as long as a PI-based or cobicistat-boosted regimen is not initiated.

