6.3.12 Pharmacokinetic Samples

PK Monitoring of Sirolimus

Trough sirolimus levels (whole blood) will be collected 4 days after administration of the first dose of sirolimus and will be analyzed and reported in real time. Trough samples will then be drawn twice a week (approximately days 4 and 7 of each week) for up to 4 weeks until two consecutive drug levels fall within 5-10 ng/mL. Once two consecutive levels fall within 5-10 ng/mL (which may be achieved before the 4-week time point after sirolimus is initiated), trough samples will be drawn every 4 weeks until study week 32 (see section 6.1.1).

The windows for PK sampling are ± 1 day through week 16 and ± 1 week for weeks 18 through 32.

Stored Plasma for PK Exposure Estimates of ARVs

In addition to real-time sirolimus testing, stored plasma will be collected for batched analysis of ARV drug concentrations.

PK Dosing Restrictions

Participants having PK sampling should be instructed to hold their morning doses of sirolimus and ARVs so a trough sample can be collected. Once trough samples have been collected, **participants** can take their normal morning doses of sirolimus and ARVs. For **participants** taking EFV, the evening dose can be taken and the time of the last dose recorded when **participants** come to the clinic for PK blood draws.

PK Data Collection

For sirolimus and ARV PK collection visits, food intake, and date, time and amount of the last three doses of sirolimus and ARVs will be recorded on the CRF.

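### An ART change during sirolimus that crosses the two starting-dose classes prompts no extra trough, so an off-target level can wait up to 4 weeks (6 with stretched windows) to be detected

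*Protocol*

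**What the plan says.** **Dose classes.** Protocol 5.1 sets the starting dose by ART class. "Participants taking an NNRTI containing regimen (with the exception of RPV) will initially receive" 0.05 mg/kg/day; participants on other permitted regimens, including rilpivirine, start at 0.025 mg/kg/day. The reason is in 2.1.10: "Drugs that could decrease sirolimus concentrations include carbamazepine, phenobarbital, phenytoin, rifapentine, NNRTIs".

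**Changes in the lead-in.** The 5.1 note from Clarification Memo #1 says "If there is a change in ART regimen between entry and week 12, the site must contact the A5337 core team", so that the starting dose can be reconsidered at week 12.

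**Changes on treatment.** Section 5.4.1 requires ART through week 44 and adds: "Changes in the regimen are allowed as long as a PI-based or cobicistat-boosted regimen is not initiated". Section 4.2.3 excludes people who intend to modify ART.

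**What covers the treatment period.**
- Section 5.4 makes investigators consult product information when a concomitant drug is started or its dose changed, "to obtain the most current information on drug interactions, contraindications, and precautions". It names no trough and no dose action.
- Once two consecutive levels are 5-10 ng/mL, "trough samples will be drawn every 4 weeks until study week 32" (6.3.12), with windows of ±1 week from week 18.
- Table 4 moves the dose by 25% for levels below 5 or between 10 and 15 ng/mL. Between 15 and 20 the instruction is "Hold dose for 48 hours, then decrease dose by 25" per cent. Above 20, drug is held until the next level and restarted at half dose if that level is below 12.
- The core team receives regular dosage and trough summaries, and the Study Monitoring Committee reviews both (9.5).

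**The concern.** The interaction behind the two-fold dose difference does not end at week 12, but the duty to contact the core team does. A participant who leaves efavirenz for an integrase inhibitor at week 21 keeps a dose titrated against an inducer that is no longer there. The opposite switch leaves a dose that may be too low. Section 10.2 names both kinds of drug among the most commonly prescribed.

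Four-weekly sampling with 25% steps suits a stable regimen. After a change between dose classes it is slow, although the trial already has a faster tool in the twice-weekly sampling used at the start of treatment.

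At stake is mainly safety: 2.1.5 says the risk of interstitial lung disease may increase with trough concentration. In the other direction, a participant could be under target for several weeks and still be analysed as a full 20-week completer.

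**Working it through.** The plan gives no figure for this delay, so there is none to reproduce. The steps below follow its dosing and sampling rules.

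**Inputs from the documents.** Dose ratio 0.05/0.025 = 2 (5.1). Half-life about 62 h (2.1.8). Target 5-10 ng/mL, Table 4 steps and rounding up to 0.5 mg (5.1). Troughs at weeks 20, 24, 28 and 32, ±1 week (6.1.1, 6.3.12). Results ideally within 72 h (3.0). At least 7 days between dose changes (2.1.9).

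**Assumed.** The exposure ratio on leaving an NNRTI: 1.25, 1.5 or 2. The documents give no interaction size. The dose rule implies 2, but 2.2.5 says of three NNRTI users in the Kaposi sarcoma study that "these participants were on steady-state doses of sirolimus that mirror those of HIV-negative participants not on ART", so a ratio near 1, with no excursion, is possible. The change is taken to act at once.

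**Step 1: delay to the first check.** Nominal gap after week 20: 24 − 20 = 4 weeks. With the windows stretched: (24 + 1) − (20 − 1) = 6 weeks. The new level is 90% reached in 62 × log2(10) / 24 = 8.6 days, so a check within about two weeks would already show it.

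**Step 2: number of corrections.** Undoing a doubling by 25% cuts takes ln 0.5 / ln 0.75 = 2.4 cuts. Undoing a halving by 25% increases takes ln 2 / ln 1.25 = 3.1.

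**Step 3: one participant.** Weight 71-90 kg, 4 mg with an NNRTI, prior trough 7.5, ratio 2, switch just after the week 20 trough.
- Week 24: 7.5 × 2 = 15.0, approached from below. Dose 4 × 0.75 = 3 mg.
- Week 28: 15 × 3/4 = 11.3. Dose 3 × 0.75 = 2.25, rounded up to 2.5 mg.
- Week 32: 15 × 2.5/4 = 9.4.
- The level passes 10 after 62 × log2(7.5/5) = 36 h (1.5 days). It falls back below 10 at 62 × log2(1.875/0.625) = 98 h (4.1 days) after the second cut, which comes at day 56 + 3 = 59. Time above 10: 59 + 4.1 − 1.5 = 61.6 days, or 8.8 weeks.

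**Step 4: average over prior troughs spread evenly from 5 to 10 (simulation of the same rules).**

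| Weeks above 10 ng/mL after leaving an NNRTI | ratio 1.25 | 1.5 | 2 |
|---|---|---|---|
| Planned schedule, switch just after week 20 | 1.7 | 3.9 | 8.4 |
| Planned schedule, switch at random in weeks 14-32 | 0.8-1.0 | 2.1-2.3 | 4.4-5.0 |
| Twice-weekly restart, switch just after week 20 | 0.4-0.7 | 1.1-1.4 | 2.4-2.9 |

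Ranges reflect different codings of sampling and adjustment times. At ratio 2 with the planned schedule and a switch just after week 20, about half of prior troughs lead to a level above 15 ng/mL. For a switch onto an NNRTI just after week 20, time below 5 ng/mL is 1.2, 2.9 or 7.0 weeks; at a random time it is about 1, 2 or 4 weeks.

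**The case against.** The strongest reply is that the note is limited to the lead-in for a good reason. It concerns the starting dose; after week 12 the measured trough sets the dose, whatever the ART class. Sampling and Table 4 run to week 32, the core team sees trough summaries, and respiratory symptoms are checked at each visit, with drug held for Grade 2 dyspnea (7.2.2). Most of this stands. It means the excursion will normally be found; it does not make it found promptly. The 5.4 review is worded for starting a drug or changing its dose. It does not expressly cover the loss of an inducer, and it requires no sample.

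Two further points stand. Just after week 20 is an unfavourable time to switch, so a random switch time is also shown. And the detailed dosing table and the precautionary-medication list sit on a study web page outside these documents, so guidance for on-treatment changes may exist there.

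A reader might infer that an on-treatment ART change leaves dosing without any review. The documents do not support that, for the reasons above.

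A reader might also infer that the average trough in SAP 14 hides such excursions and so distorts the findings. It can hide one: with 10 earlier troughs at 7.5, the participant in step 3 averages (75 + 15.0 + 11.3 + 9.4)/13 = 8.5, inside target. But this depends on the starting level. At ratio 2, between 24% and 38% of evenly spaced prior troughs give an average outside 5-10 ng/mL. The average is a descriptive summary with exploratory correlations, and no primary result rests on it.

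**Conclusion.** The concern holds as a gap in timely detection. After an on-treatment change across dose classes, the visible plan requires neither core-team contact nor an event-driven trough. The next check can be 4 weeks away (6 with stretched windows), and correction then proceeds mostly by 25% at a time. If leaving an NNRTI raises exposure 1.25, 1.5 or 2 times, the average time above 10 ng/mL is roughly 1, 2.3 or 5 weeks for a switch at a random time, and 1.7, 3.9 or 8.4 weeks for one just after week 20. Returning to twice-weekly sampling removes about two-thirds of the latter.

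These figures apply per participant who changes class. They rest on an assumed ratio that may be near 1, and few such changes are expected because intended ART modification is excluded. The documents do not show that any occurred. The primary efficacy set, test and power are unaffected. The case for acting is participant safety at low cost.

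**What to change.** **Protocol 5.1 note, add:** for any ART change between weeks 12 and 32, the site contacts the core team before the new regimen starts, or as soon as the change is known. If the change crosses the 0.025/0.05 mg/kg classes, trough sampling returns to the existing twice-weekly schedule until two consecutive levels are 5-10 ng/mL, with dose set by Table 4. Automatic halving or doubling is not advised, because the true ratio is uncertain.

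**Cost:** one addition to the note and a few extra trough draws per class-changer (in the week 20 case, about 6 to 9 troughs in place of 3).

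**Optional, SAP 13.2:** in the planned listing of gaps and holds, show on-treatment ART regimen changes (old and new regimen, treatment week) with that participant's troughs before and after. ART modifications are already recorded (Protocol 6.3.4). This is descriptive and changes no conclusion. SAP 5.3 already counts 16 participants with the full 20 weeks of sirolimus, so for data already collected only this listing can still be applied; the protocol addition serves further dosing or a later trial.

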6.2.3 Event Driven Evaluations

Confirmation visit to confirm CD4+ cell count <300 cells/mm³ or >50% CD4+ decrease from study entry value or HIV-1 RNA >200 copies/mL (see sections 7.1.4 and 7.1.5) should be scheduled within 1 week of receipt of the abnormal lab value. If confirmed CD4+ cell count <300 cells/mm³ or >50% CD4+ decrease from study entry value or HIV-1 RNA >200 copies/mL, the study team should be promptly contacted and sirolimus should not be started or should be stopped if already started.

NOTE: If study entry CD4+ cell count is not available, monitoring for >50% decrease should be done relative to the week 12 CD4+ cell count. If neither entry nor week 12 CD4+ cell count is available, monitoring for >50% decrease should be done relative to the screening CD4+ cell count.

A5337

**Safety and Efficacy of Sirolimus for HIV Reservoir Reduction in Individuals on
Suppressive Antiretroviral Therapy**

A Limited Center Trial of the AIDS Clinical Trials Group (ACTG)

Sponsored by:

**The National Institute of Allergy
and Infectious Diseases**

Industry Support Provided by:

ViiV Healthcare

**The ACTG HIV Reservoirs and Viral Eradication
Transformative Science Group:** [name], Chair

Protocol Co-Chairs: [name]
[name]

Protocol Vice Chair: [name]

DAIDS Clinical Representative: [name]

Clinical Trials Specialist: [name], MA

**Version 2.0
July 18, 2016**

CONTENTS

	Page
SITES PARTICIPATING IN THE STUDY	4
PROTOCOL TEAM ROSTER	5
STUDY MANAGEMENT	8
GLOSSARY OF PROTOCOL-SPECIFIC TERMS	10
SCHEMA	11
1.0 HYPOTHESES AND STUDY OBJECTIVES.....	13
1.1 Hypotheses.....	13
1.2 Primary Objectives.....	13
1.3 Secondary Objectives.....	13
1.4 Exploratory Objectives.....	13
2.0 INTRODUCTION.....	14
2.1 Background.....	14
2.2 Rationale	20
3.0 STUDY DESIGN	25
4.0 SELECTION AND ENROLLMENT OF PARTICIPANTS	26
4.1 Inclusion Criteria	26
4.2 Exclusion Criteria.....	28
4.3 Study Enrollment Procedures.....	30
4.4 Coenrollment Guidelines.....	31
5.0 STUDY TREATMENT	32
5.1 Regimens, Administration and Duration	32
5.2 Study Product Formulation and Preparation.....	33
5.3 Pharmacy: Product Supply, Distribution, and Accountability	34
5.4 Concomitant Medications	34
6.0 CLINICAL AND LABORATORY EVALUATIONS.....	36
6.1 Schedule of Events	36
6.2 Timing of Evaluations.....	39
6.3 Instructions for Evaluations	41
7.0 CLINICAL MANAGEMENT ISSUES	49
7.1 Toxicity	49
7.2 Management of Specific Toxicities.....	51
7.3 Management of HPV-Related Disease.....	52
